#### **7.5.3. Definition of Maximum Tolerated Dose**

The MTD is defined as the highest dose level at which  $\leq 1$  of 6 patients experiences DLT through 30 days post-ASCT.

[figure not shown]
#### **7.5.4. Definition of Recommended Phase 2 Dose**

The RP2D may be equal to or higher than the preliminary MTD, but less than the non-tolerated dose (i.e., the dose at which  $\geq 2$  of 6 patients experienced DLT). The RP2D will be determined in discussion with the Sponsor, Medical Monitor, and Investigators.

### **7.6. Study Drug Preparation and Administration**

#### **7.6.1. Study Drug Preparation**

For administration, tinostamustine powder is reconstituted with 20 mL saline (0.9%) and the solution must be further diluted with saline (0.9%) to a final volume of 50 mL. **CCI**

[figure not shown]

Please refer to the study specific Pharmacy Manual to ensure the correct preparation of tinostamustine.

### **7.6.2. Study Drug Administration**

Tinostamustine is to be administered IV through a peripheral vein over 1 hour.

CCI

CCI

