11. A triplicate ECG will be performed during Screening to determine patient eligibility for the study. Furthermore, on Day -1, a triplicate ECG is to be performed before study drug administration and a single ECGs will be performed at 30 and 60 minutes after the start of study drug administration for assessment by the site. Another single ECG will be performed at visit on day 30 ( $\pm 5$  days). ECGs are to be repeated by the Investigator, as clinically indicated.
12. Hematology parameters minimally include WBC count and differential (lymphocytes, monocytes, basophils, eosinophils, neutrophils), red blood cell (RBC) count, hematocrit, hemoglobin, and platelet count.
13. Serum chemistry parameters minimally include alanine aminotransferase (ALT), albumin, alkaline phosphatase (ALP), aspartate aminotransferase, (AST), bicarbonate, bilirubin (total, direct, and indirect), calcium, magnesium, chloride, glucose, lactate dehydrogenase (LDH), phosphate, potassium, sodium, and total protein.
14. Urinalysis includes appearance, color, pH, specific gravity, ketones, leukocytes, protein, glucose, bilirubin, urobilinogen, and occult blood.
15. The tinostamustine dose will be administered one day before ASCT (Day -1), at least 24 hours pre-ASCT.
16. Blood samples for PK are to be collected immediately pre-infusion of tinostamustine and 30, 45, and 60 ( $\pm 5$ ) minutes and then at 3, 6, and 24 hours ( $\pm 15$  minutes) and then 48 hours ( $\pm 30$  minutes) after the start of infusion. Blood samples for PK assessment should be collected following the 15-minute supine resting periods described for the continuous Holter recordings. PK samples are to be collected from the arm opposite of that used for tinostamustine administration.
17. On Day 1, ASCs will be administered IV according to standard institutional practice. If the CD34+ product is of large volume, the infusion can be given over 2 days.
18. A skeletal survey (plain radiographs, or any other method used as standard care at the site, of the skull, spine, ribs, pelvis, humeri and femora) will be performed at Screening if not performed within the previous 3 months. Thereafter, skeletal survey and/or other imaging studies are to be performed as clinically indicated.
19. Bone marrow aspirate and trephine biopsy are to be performed during Screening. Bone marrow aspirate and biopsy are to be repeated during treatment as clinically indicated, at the Investigator's discretion, and at any time CR is suspected.

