#### **9.4. Pharmacokinetics**

Serial blood samples for PK analysis will be collected after each tinostamustine dose according to the schedule in [Table 1](#). Blood samples for PK assessment should be collected following the 15-minute supine, resting periods described for the continuous Holter recordings. PK samples are to be collected from the arm opposite of that used for tinostamustine administration.

The calendar date and exact 24-hour clock time of blood sample collection for PK assessments will be documented in the source document and the eCRF.

Samples will be collected, labelled, stored and shipped as detailed in the Laboratory Manual.

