#### **10.2.9. Pharmacokinetic Analyses**

PK analysis for tinostamustine and its metabolites will be performed using the PK set.

PK parameters at all doses will include  $C_{max}$ , time to maximum plasma concentration ( $t_{max}$ ),  $t_{1/2}$ , area under the plasma concentration curve from 0 to 12 hours ( $AUC_{0-12}$ ), area under the plasma concentration curve from time 0 to time t ( $AUC_{0-t}$ ), apparent total clearance (CL/F), apparent volume of distribution (Vd/F), and terminal disposition rate constant ( $\lambda_z$ ). The initial calculation of PK parameters will be performed using non-compartmental analysis. Plasma concentrations and PK parameters will be summarized by dose.

Summaries will include the number of observations (n), arithmetic or geometric mean, SD or coefficient of variation (CoV), median, minimum, and maximum.

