
Storer BE. Design and analysis of phase I clinical trials. *Biometrics* 1989;45(3):925-37.

**Date:** September 21, 2018

**To:** EDO-S101-1004 (TITANIUM 1) Investigators and Site Staff

**Protocol Title:** A Phase 1/2 Open-Label Trial of Tinostamustine Conditioning and Autologous Stem Cell Transplant for Salvage Treatment in Relapsed/Refractory Multiple Myeloma (TITANIUM 1)

**Protocol Version:** 2.0, 18 June 2018

**Subject:** Protocol Clarification Memo

---

Dear Investigators and Site Staff,

Please see below clarifications for EDO-S101-1004 version 2.0 protocol from 18 June 2018.

**Item 1:** Use of central line

Currently, Protocol Version 2.0 18 June 2018 states on the bottom of page 11, that Tinostamustine will be administered by IV infusion through a peripheral vein over 1 hour. This is also noted in section 7.6.2 on page 49.

It should say that Tinostamustine will be administered by IV infusion through a peripheral vein or a central line over 1 hour.

**Item 2:** Day of Autologous Stem Cell Transplant (ASCT)

Currently, Protocol Version 2.0 18 June 2018 states in the header of the Schedule of Events on pages 17 and 18, that ASCT is on Day 0.

It should say that the day of ASCT is study Day 1.

**Item 3:** Exclusion Criteria #2

Currently, Protocol Version 2.0 18 June 2018 has two Exclusion Criteria #2's listed on page 39. The one noted as "Primary or secondary plasma cell leukemia at any point prior to transplant" is not noted in the Clinical Study Synopsis exclusion criteria list on page 10.

This exclusion criteria should be included in the Clinical Study Synopsis.

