**Recommended Anti-Emetics**

Due to its association with QTc prolongation, ondansetron is prohibited around the time of tinostamustine dosing. Also, due to reported interactions with alkylating agents, aprepitant is also not allowed for nausea control. We, therefore, recommend the following anti-emetic medications for nausea control on day -1:

- Palonosetron
- Glucocorticoids-as single agent or in combination with palonosetron
- Olanzapine
- Lorazepam-in combination with other recommended anti-emetics

Given the short half-life of tinostamustine, ondansetron can be used up to 24 hours prior to tinostamustine dosing on day -1 and resumed 24 hours after the dose. In patients with mild hepatic dysfunction, this interval should be extended to 48 hours due to reports of delayed clearance of ondansetron in this population. Since aprepitant has a long half-life, it should not be administered at least 3 days prior to tinostamustine dosing. If needed, aprepitant can be given 24 hours after tinostamustine dosing.

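### The 60 (±5)-minute PK sample straddles the end of the 1-hour infusion, adding modest, avoidable sampling-time noise to Cmax and tmax

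*Protocol*

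**What the plan says.** Section 7.6.2 of Protocol version 2.0 reads "Tinostamustine is to be administered IV through a peripheral vein over 1 hour". The clarification memo of 21 September 2018 widens the route but keeps the duration: "It should say that Tinostamustine will be administered by IV infusion through a peripheral vein or a central line over 1 hour".

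Table 1, footnote 16, sets the PK samples: "Blood samples for PK are to be collected immediately pre-infusion of tinostamustine and 30, 45, and 60" minutes with a ±5-minute window, then 3, 6 and 24 hours (±15 minutes) and 48 hours (±30 minutes). All are counted "after the start of infusion. Blood samples for PK assessment should be collected following the 15-minute supine resting periods" that footnote 9 describes for the Holter recordings.

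Section 9.4 gives no times of its own: "Serial blood samples for PK analysis will be collected after each tinostamustine dose according to the schedule in" Table 1. It does require the exact clock time of each blood sample.

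Section 10.2.9 lists Cmax and tmax among the parameters, starts from non-compartmental analysis, and adds "Plasma concentrations and PK parameters will be summarized by dose". SAP section IX leaves PK to a separate third-party report. No half-life figure appears. The memo of 30 January 2019 says only "Given the short half-life of tinostamustine".

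**The concern.** With a constant-rate infusion and a drug that clears quickly, concentration rises until the infusion stops and then falls. The sample meant to catch the peak may be taken from minute 55 to minute 65, and the infusion nominally stops at minute 60. Nothing in the visible text says whether the draw comes before or after the stop, or ties it to the actual stop. Two patients who both follow the schedule can therefore be sampled on opposite limbs of the curve, and no further sample is due until 3 hours.

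Under non-compartmental analysis Cmax is the largest measured value and tmax is the time of that sample. Recorded clock times help AUC and show when a sample was taken, but they do not recover a peak that nobody sampled. PK is the only secondary objective of Phase 1, and dose cohorts hold 3 to 6 patients.

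**Working it through.** **Inputs from the documents.** Infusion length T = 60 minutes (7.6.2). Samples at 30, 45 and 60 (±5) minutes, then 3 hours (footnote 16). Dose levels 180, 220, 260 and 300 mg/m² (7.5). The plan states no PK precision figure, so there is none to reproduce.

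**Step 1: the window.** 60 − 5 = 55 and 60 + 5 = 65. The stop at minute 60 lies inside the window. This step needs no assumption.

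**Step 2: the size.** Assumptions: one compartment, constant rate, and half-life h between 10 and 120 minutes, because the documents give none. With k = ln 2 / h:

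- up to the stop, C(t) ∝ 1 − exp(−kt)
- after it, C(t) ∝ [1 − exp(−60k)] × exp(−k(t − 60))

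Observed Cmax is the largest of the 30-, 45-, nominal 60- and 180-minute values, divided by the true value at minute 60.

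Example, h = 26 minutes:

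- C(60) ∝ 1 − 2^(−60/26) = 0.798
- C(45)/C(60) = 0.699/0.798 = 0.876
- C(55)/C(60) = 0.769/0.798 = 0.964
- C(65)/C(60) = 2^(−5/26) = 0.875

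A draw at 65 minutes gives 0.875, slightly below the 45-minute sample. Observed Cmax is therefore 0.876 of the true value and tmax is read as 45 minutes.

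In the table, every figure except the SD is a ratio to the true end-of-infusion level. Worst, mean and SD refer to observed Cmax. Mean and SD assume draws spread evenly over 55 to 65 minutes.

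| h (min) | C(45) | C(55) | C(65) | Worst, ±5 | Mean, ±5 | SD, ±5 | Worst, −5 to 0 | Worst, −2 to 0 |
|---|---|---|---|---|---|---|---|---|
| 10 | 0.971 | 0.993 | 0.707 | 0.971 | 0.985 | 1.3% | 0.993 | 0.998 |
| 20 | 0.903 | 0.973 | 0.841 | 0.903 | 0.959 | 3.6% | 0.973 | 0.990 |
| 26 | 0.876 | 0.964 | 0.875 | 0.876 | 0.959 | 3.5% | 0.964 | 0.986 |
| 30 | 0.862 | 0.959 | 0.891 | 0.891 | 0.962 | 3.0% | 0.959 | 0.984 |
| 60 | 0.811 | 0.941 | 0.944 | 0.941 | 0.971 | 1.7% | 0.941 | 0.977 |
| 120 | 0.781 | 0.929 | 0.972 | 0.929 | 0.975 | 1.9% | 0.929 | 0.972 |

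- **Single patient, worst case:** 3% to 12% low. The extreme is near h = 26 minutes. If the ±5 also covers the 45-minute sample and it is drawn at 40, the extreme is 0.850 (15% low) near h = 21 minutes.
- **Average over the window:** about 1.5% to 4% low. The SD is at most about 3.6% at the half-lives shown; a fine scan peaks at 3.8% near 22.5 minutes.
- **tmax after a 65-minute draw:** read as 45 minutes for half-lives up to about 26 minutes and as 65 above that.

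**Step 3: against the dose steps.** 220/180 = +22%, 260/220 = +18%, 300/260 = +15%. Timing noise on a cohort mean is about 3.6%/√3 = 2.1% with 3 patients and 3.6%/√6 = 1.5% with 6.

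**The case against.** A reader might set the 12% figure beside a 15% to 22% dose step and infer that timing can cost half a step or more. The documents do not support that. The 12% is one patient's worst case. It needs a draw at the edge of the window and a half-life near 26 minutes, which the documents do not give. The window is the same at every dose, so under linear kinetics the average bias is a common proportion and largely cancels in a dose-to-dose ratio. What remains is about 1.5% to 2% noise on a cohort mean, before any between-patient variability. This objection stands and sets the scale of the point.

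A reader might also infer that tmax loses information about dose. In this model true tmax is the end of infusion at every dose, so no dose signal is lost. tmax is simply recorded wrongly.

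A third inference would be that the stop time is not captured, or that the data cannot be repaired. Neither can be established. Text is redacted directly after the sentence in 7.6.2, collection details sit in a Laboratory Manual, and non-compartmental analysis is only the initial calculation, which leaves room for a model using actual times.

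Finally, the consequence is small. Escalation, the MTD and the ceiling on the RP2D rest on DLTs, PK is descriptive, and SAP section I.C records that the study was halted and later discontinued. All of this is fair. None of it removes the straddling window.

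**Conclusion.** The point holds as a minor design improvement. That a compliant sample may fall on either side of the infusion stop follows from the text alone. The size rests on a one-compartment model and assumed half-lives of 10 to 120 minutes: single-patient Cmax at worst about 3% to 12% low, an average shortfall of about 1.5% to 4% with an SD of about 3.6% or less, and tmax that can read 45 or 65 minutes from timing alone. This is modest noise in the dose-exposure summary. It is not an error of half a dose step, and it has no bearing on escalation, the MTD or the primary endpoint.

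**What to change.** Change footnote 16 only, since section 9.4 merely points to Table 1. Replace the 60 (±5)-minute PK sample with an end-of-infusion sample drawn immediately before the actual stop, for example −2 to 0 minutes. Record the actual stop time, start the supine rest early enough that the draw follows it, and leave the other samples and the infusion itself unchanged.

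In the same model the worst-case Cmax shortfall is then under 3% at every half-life tried, the largest being 1 − 0.972 = 2.8% at 120 minutes. A looser −5 to 0 window is not enough: it keeps the 55-minute draw and does not improve the worst case at half-lives of 60 minutes or more.

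The cost is one footnote and one eCRF time field, with no added sample or visit. The downsides are a tighter draw window for staff and, if the infusion runs short or long, a small separation between the PK draw and the 60-minute Holter timepoint.

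Because the study was discontinued, the schedule change matters only for a resumed or later protocol that reuses it. For data already collected, the separate PK report should state, where records allow, whether each nominal 60-minute sample was taken before or after the infusion stopped, and qualify Cmax and tmax accordingly.

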## 7.8. Prior and Concomitant Medications and Procedures

All prescription and non-prescription medications and therapies, including pharmacologic doses of vitamins, herbal medicines, or other non-traditional medicines, taken from 28 days prior to the first dose of tinostamustine through Day 100 ( $\pm 7$  days) must be recorded in the eCRF.

Concomitant medications will be documented as administered pre-conditioning (i.e., pre-tinostamustine); during conditioning (i.e., after the start of the first tinostamustine infusion through immediately before the start of autologous stem cell [ASC] infusion); or after ASCT (i.e., after the start of ASC infusion).

On PK sample collection days (Table 1), both the date and time of concomitant medications and therapies must be recorded.

The Investigator should contact the study medical monitor with any questions or clarifications regarding concomitant medications.

### **7.8.1. Prohibited Medications**

The following medications and treatments are prohibited during study participation:

- Any investigational agent or device other than tinostamustine, including agents that are commercially available for indications other than MM that are under investigation for the treatment of MM.
- Any anti-neoplastic treatment with activity against MM.
- Medications known to prolong the QT/QTc interval, will be excluded. The use of other concomitant medications that present a low risk of QT/QTc prolongation may be considered, with the approval of the Medical Monitor. (Refer to the crediblemeds list of drugs with known risk of TdP: <http://crediblemeds.org>.)

### **7.8.2. Permitted Medications and Supportive Therapies**

Medications and treatments other than those specified in Section 7.8.1, including palliative and supportive care for disease-related symptoms, are permitted during the study. Patients should be closely monitored, and treatment is to be instituted for disease-related symptoms, as appropriate.

Patients may receive the following supportive care:

- IV hydration and anti-emetics, in accordance with institutional guidelines.
- Growth factor support with pegfilgrastim or equivalent agent post-ASCT, in accordance with institutional guidelines.
- Standard supportive care, in accordance with institutional guidelines, including blood product transfusions, antimicrobial prophylaxis (e.g., anti-bacterial, *Pneumocystis carinii*, anti-fungal, herpes simplex virus/varicella zoster virus), and treatment for febrile neutropenia.
- Bisphosphonates may be administered after ASCT according to local institutional practice.
- After adequate blood count recovery (ANC  $>1.0 \times 10^9/L$  and platelet count  $>80 \times 10^9/L$ ) as well as resolution of mucositis and fever, if present, radiation may be administered for the following indications after consultation with the Medical Monitor:
  - Palliation of pain from bone lesions
  - Prevention of pathologic fractures
  - Relief of spinal cord compression or nerve root compression

The radiation oncologist is to determine the dose and duration of radiation to be administered. Radiation to the liver or lungs should be avoided.

## **7.9. Blinding**

This is an open-label study; no blinding methods will be employed.

## **8. TRANSPLANT PROCEDURES**

### **8.1. Conditioning**

See [Section 7.6](#) for details regarding tinostamustine preparation and administration.

### **8.2. ASCT Infusion**

Patients will receive ASCs on Day 1. The ASCs will be infused via a central venous catheter using standard blood infusion tubing, per standard institutional practice.

### **8.3. Engraftment**

During in-patient hospitalization, patients will be assessed daily for hematologic engraftment, starting on the first day the ANC is  $<0.5 \times 10^9/L$  until and including the day engraftment criteria are met, as follows:

- Neutrophil engraftment is defined as the first of 3 consecutive days with ANC  $>0.5 \times 10^9/L$ .
- Platelet engraftment will be defined as the first of 3 consecutive days of platelet count  $>20 \times 10^9/L$  without platelet transfusion in the prior 7 days.

## **9. STUDY ASSESSMENTS**

### **9.1. Baseline Assessments**

#### **9.1.1. Informed Consent**

All patients must provide written informed consent before any samples are collected or evaluations performed in this study that are not part of standard patient care.

#### **9.1.2. Demographics**

Patient demographics, including age, sex, race, and ethnicity, are to be documented in the source documents and in the eCRF at Screening.

#### **9.1.3. Medical History, Including Cancer History**

A complete medical history, including prior and concomitant illnesses and conditions as well as prior surgeries and other procedures, is to be documented in the source documents and in the eCRF at Screening. MM history, including the date of diagnosis and details regarding prior ASCT and all other previous treatment for MM and best response to such treatments, also is to be documented and recorded in the eCRF.

#### **9.1.4. Hematopoietic Cell Transplantation-Comorbidity Index (HCT-CI)**

The HCT-CI is a validated comorbidity index that comprises 17 different categories of organ dysfunction (Sorror et al. 2007; Maruyama et al. 2007; Barba et al. 2010; Frina et al. 2009). Positive findings are summated into a total score. The HCT-CI provides information with regard to the overall as well as non-relapse mortality risk a patient is likely to experience after SCT. HCT-CI score is to be documented in the source documents and in the eCRF at Screening.

The HCT-CI is accessible at: <http://www.hctci.org/Home/Calculator>.

#### **9.1.5. Prior and Concomitant Medications**

All prior medications and supplements the patient received within 28 days before baseline and all medications and supplements the patient receives through Day 100 are to be documented in the source documents and in the eCRF. Concomitant medications will be documented as administered pre-conditioning (i.e., pre-tinostamustine); during conditioning (i.e., after the start of the first tinostamustine infusion through immediately before the start of ASC infusion); or after ASCT (i.e., after the start of ASC infusion).

#### **9.1.6. Echocardiogram or Multi-gated Acquisition Scan**

LVEF is to be determined by multi-gated acquisition scan or echocardiography during Screening.

### **9.1.7. Pulmonary Function Testing**

The following PFTs are to be measured during Screening

- FEV1
- FVC
- DLCO

Patients who have difficulty making an appropriate seal on the mouthpiece to perform PFTs effectively should be fitted with a facial mask for PFT measurements.

### **9.1.8. Screening Serologies**

Blood samples for infectious disease marker testing, including, at a minimum, human immunodeficiency virus (HIV) types 1 and 2, hepatitis B virus (HBV) panel (HBV surface antigen, HBV surface antibody, HBV core antibody, HBV e-antigen), hepatitis C virus (HCV), *Treponema pallidum*, cytomegalovirus, and Epstein-Barr virus, are to be collected during Screening. Any patient with a positive result is not eligible for study participation.

### **9.1.9. Pregnancy Testing**

Serum or urine  $\beta$ -human chorionic gonadotropin (hCG) pregnancy testing is to be performed for female patients of childbearing potential (i.e., premenopausal or not surgically sterile) during Screening. Any patient with a positive result is not eligible for study participation. Pregnancy testing is to be repeated any time pregnancy is suspected.

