2. Written informed consent is to be obtained before the performance of any study-related procedures.
3. Pulmonary function testing is to include FEV1, FVC, and DLCO.
4. Infectious disease marker testing is to include, at a minimum, human immunodeficiency virus (HIV) types 1 and 2, hepatitis B virus (HBV) panel (HBV surface antigen, HBV surface antibody, HBV core antibody, HBV e-antigen), hepatitis C virus (HCV), Treponema pallidum, CMV, and Epstein-Barr virus.
5. Urine or serum pregnancy testing will be performed for women of childbearing potential. Pregnancy testing is to be repeated on study any time pregnancy is suspected.
6. Vital signs include blood pressure, pulse, respiratory rate, and temperature. Vital signs are to be measured after patient is sitting for 3-5 minutes.

7. Perform assessment both pre- and post-treatment.
8. ECGs (12-lead) are to be performed after the patient is supine for 5 minutes. Repeat ECGs as clinically indicated. Screening ECGs will be reviewed centrally. Regarding other 12 lead ECGs: the investigator or the sponsor may request expedited central review of ECGs, as clinically indicated.
9. Continuous Holter monitoring will be performed on Day -1, the day of tinostamustine administration. Holter monitoring will commence 15 minutes prior to the start of the infusion on Day -1 and will continue through 24 hours following the end of infusion. Patients should be resting comfortably in the supine or semisupine position for 15 minutes prior to each of the following timepoints: 0 [before start of infusion] then after start of the infusion at 15, 30, 45, and 60 minutes and 3, 6, and 24 hours following the start of the infusion. At time 0 and at all time points after infusion, ECGs readings will be extracted in triplicate, with each ECG separated by 5 minutes ( $\pm 2$  minutes), for establishment of baseline for the purposes of cardiac safety analyses. The Holter monitor flashcards will be sent to eResearch Technology, Inc., for processing.
10. The Investigator's interpretation of ECGs is to be used for patient management during the study; the central reader interpretation of ECGs extracted from Holter monitoring will be used to determine all ECG data for study endpoints including baseline QTcF interval for cardiac safety analyses and DLTs.

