### **6.4. Treatment Discontinuation Criteria**

Once tinostamustine has been infused it will be medically negligent to stop transplant and supportive therapy for the particular patient. In the event of consent withdrawal during or following conditioning or the development of complications that, in the Investigator's opinion, puts the patient at risk with continued protocol-specified treatment, the Medical Monitor should be contacted immediately to discuss management of the patient.

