### **9.2.8.8. Pregnancy**

Pregnancy is considered unlikely in this study, given the population of patients to be enrolled. Nonetheless, pregnancies occurring within 12 months after the patient's last dose of tinostamustine will not be considered serious, but are to be reported using the same procedures as for SAEs described in [Section 9.2.8.4](#).

The patient is to be referred to an obstetrician/gynecologist experienced in reproductive toxicity for further evaluation and counseling.

The Investigator will follow the patient until completion of the pregnancy, and must notify the Medical Monitor of the outcome within 5 days. The Investigator will provide this information as a follow-up to the initial report.

If the outcome of the pregnancy meets the criteria for immediate classification as an SAE (i.e., spontaneous abortion [any congenital anomaly detected in an aborted fetus is to be documented], stillbirth, neonatal death, or congenital anomaly), then the Investigator should report it as such. Furthermore, all neonatal deaths that occur within 30 days of birth are to be reported, without regard to causality, as SAEs. In addition, any infant death after 30 days that the Investigator suspects is related to the *in utero* exposure to tinostamustine should also be reported.

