**Item 2: Day of Autologous Stem Cell Transplant (ASCT)**

Currently, Protocol Clarification memo dated 21Sep18 and Protocol Version 2.0 18 June 2018 in all places except the header of the Schedule of Events on pages 17 and 18, that ASCT is on Day 1.

As is standard practice, it should say that the day of ASCT is study Day 0.

This clarification does not impact patient safety. Please submit this clarification to your IRB/IEC for their review, if required. In addition, file this letter and any IRB/IEC correspondence in your study files.

This clarification will be incorporated into a subsequent protocol amendment should one be required.

I am available to discuss any questions or comments you may have.

PPD  
Sincerely,  
PPD

PPD            MD    PP  
D  
Mundipharma-EDO GmbH

Cc: EDO-S101-1004 Study Team  
Cc: EDO-S101-1004 Trial Master File

**Date:** 14 December 2018

**To:** EDO-S101-1004 (TITANIUM 1) Investigator and Site Staff

**Protocol Title:** A Phase 1/2 Open-Label Trial of Tinostamustine Conditioning and Autologous Stem Cell Transplantation for Salvage Treatment in Relapsed/Refractory Multiple Myeloma (TITANIUM 1)

**Protocol Version:** 2.0, 18 June 2018

**Subject:** Protocol Clarification Memo

---

Dear Investigator and Site Staff,

Please see below clarifications for EDO-S101-1004 version 2.0 protocol 18 June 2018. An amendment is forthcoming with these changes incorporated.

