*Methods that achieve a failure rate of less than 1% per year when consistently and correctly used are considered highly effective methods of birth control. Highly effective methods of birth control include: estrogen and progestogen combined hormonal contraception which inhibits ovulation, progestogen-only hormonal contraception associated with inhibition of ovulation, intrauterine devices (IUD), bilateral tubal occlusion, vasectomized partner in a monogamous sexual relationship, and complete sexual abstinence. Acceptable, but less effective (>1% failure rate per year) methods such as male or female condom with spermicide, cap, diaphragm, or sponge with spermicide, or double barrier methods may be used in conjunction with another form of highly effective birth control.*

**Item 6:** Duration of contraception requirement, Section 5 “Study Population” New Sub-Section

Currently, Protocol Version 2.0 18 June 2018 does not provide a proposed duration for the contraception requirement. The protocol will be amended to include the following text:

*Males and females of child bearing potential, and their partners, must be willing to use at least two effective forms of birth control for at least ninety (90) days after the administration of the study drug to be eligible to participate. These requirements were created based on the recommendations by the Clinical Trial Facilitation Group (CTFG) “Recommendations related to contraception and pregnancy testing in clinical trials” (15Sep2014) due to the alkylating nature of the drug and the limited data on genetotoxicity.*

**Item 7:** Contraception Eligibility, Synopsis Pg.10; Pg. 39 Section 5.1

Currently, Protocol Version 2.0 18 June 2018 does not include guidance on pregnancy, contraception and eligibility. The following protocol inclusion criteria will be updated to include the following text to the above sections.

*12. Males and females of child bearing potential, and their partners, must be willing to use at least two effective forms of birth control for at least ninety (90) days after the administration of the study drug to be eligible to participate.*

**Item 8:** Exclusion criteria #9, Synopsis Pg.11; Pg. 39 Section 5.2

Currently, Protocol Version 2.0 18 June 2018 states that patients who are found to be pregnant, are not eligible. Current exclusion criteria number 9 will be updated with the below language.

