11. Potassium within the local laboratory's normal range. (Potassium supplementation is permissible.)
12. *Males and females of child bearing potential, and their partners, must be willing to use at least two effective forms of birth control for at least ninety (90) days after the administration of the study drug to be eligible to participate.*

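### The only scheduled pregnancy test can precede the single Day -1 dose by up to 27 days, with no required pre-dose repeat and no stated start for contraception

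*Protocol*

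**What the plan says.** Section 9.1.9 of the protocol (Version 2.0) states that hCG "pregnancy testing is to be performed for female patients of childbearing potential (i.e., premenopausal or not surgically sterile) during Screening". Table 1 marks the test in the Screening column only, which spans D-28 to D-1. The conditioning (D-1), transplant and follow-up columns are blank for it. The one trigger for another test is clinical suspicion; footnote 5 of Table 1 reads "Pregnancy testing is to be repeated on study any time pregnancy is suspected".

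Tinostamustine is given once, on Day -1, about 24 hours before the stem cell infusion. On day numbering, the October 2018 clarification memo settles that "it should say that the day of ASCT is study Day 0".

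Version 2.0 gave no contraception guidance. The December 2018 memo added inclusion criterion 12, which requires two effective forms of birth control for "at least ninety (90) days after the administration of the study drug". It names no start. The same memo widened exclusion 9 to women who plan a pregnancy, and justified the contraception rule "due to the alkylating nature of the drug and the limited data on genetotoxicity".

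Section 9.2.8.8 gives the sponsor's view of the likelihood: "Pregnancy is considered unlikely in this study, given the population of patients to be enrolled".

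**The concern.** A negative hCG early in screening says nothing about a conception after the test, and it can miss one too recent to detect. The plan lets that test stand as the only evidence for exclusion 9 until the drug is infused. The visible text sets no contraception requirement for the interval between test and dose.

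The stake is fetal exposure to an alkylating drug. Most trials with repeated dosing can stop when a pregnancy is found. Here the whole exposure is one infusion, and section 6.4 says of the period afterwards: "Once tinostamustine has been infused it will be medically negligent to stop transplant and supportive therapy". That passage is not about pregnancy, but it confirms that a pregnancy found after dosing leaves no way back. The useful check is the one before the infusion.

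This is a patient-safety matter. It does not bear on response rate, dose-limiting toxicity or any other estimate.

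**Working it through.** The plan states no figure for the test-to-dose interval, so it has to be derived from the schedule.

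**Inputs**
- Earliest screening day: D-28 (Table 1, Screening column).
- Latest screening day: D-1 (same column).
- Dose day: D-1 (Table 1, footnote 15).
- Transplant day: Day 0 (October 2018 memo, Item 2).
- Contraception: at least 90 days after dosing (December 2018 memo, inclusion criterion 12).

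**Permitted gap between test and dose**
- Maximum = 28 − 1 = 27 days (test on D-28).
- Minimum = 1 − 1 = 0 days (test on D-1 before the infusion).
- Check from the text of section 4.1: screening may start 28 days before transplant and the dose falls 1 day before transplant, so 28 − 1 = 27 days again. Calling the transplant day Day 0 or Day 1 makes no difference to this, because the dose is tied to the transplant by 24 hours.

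**Do the other safeguards cover the gap?**

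| Safeguard | Where | What it leaves open |
|---|---|---|
| Repeat test on suspicion | 9.1.9; Table 1, footnote 5 | An unsuspected pregnancy |
| Exclusion of women who are, or plan to become, pregnant | Exclusion 9, December 2018 memo | Unplanned conception; no test date is set |
| Targeted examination on Day -1 | Table 1; 9.2.1 | Symptom-directed, so not a reliable check |
| Sponsor confirmation of eligibility before enrolment | 6.1 | No fresh hCG is required |
| Second eligibility review | Table 1, D0 column | As printed, it follows the dose |
| Contraception | Criterion 12 | The period before the dose is not stated |

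The second-review row needs care. Table 1 also leaves weight blank at D-1 and marks it at D0, although section 9.2.2 needs a weight before the Day -1 infusion to calculate the dose. The D0 marks may be misplaced. Even a review held before the dose would not by itself require a new test.

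**Effect of a timing rule.** The documents give no interval, so these are assumed for illustration:
- 7-day rule: (27 − 7) / 27 = 20 / 27 = 74% shorter maximum gap.
- 3-day rule: (27 − 3) / 27 = 24 / 27 = 89% shorter.
- Test on Day -1 before the infusion: maximum gap 0.

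These percentages describe the longest permitted gap. They are not reductions in risk, which cannot be computed from the documents.

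**Contraception period.** From consent at D-28 through 90 days after dosing: 27 + 90 = at least 117 days, against at least 90 days as now stated.

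**The case against.** The case against acting rests on how rarely this would matter. Every patient has relapsed myeloma after a previous transplant, the sponsor calls pregnancy unlikely, and Phase 1 planned only 9 to 12 patients. The number of women of childbearing potential is not given and could be zero. The SAP (section I.C) reports that the study was halted and later discontinued, so a new testing rule protects nobody in this trial. The 28-day window also governs creatinine clearance, ejection fraction, and lung and liver function. The sponsor was already tightening the reproductive provisions in December 2018. Consent pages and some protocol text are not available, and a contraception start could appear there.

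Much of this stands. Frequency is low, 27 days is the permitted extreme, and the statement about contraception holds for the visible text only. Discontinuation confines the practical value to a restart or a later protocol that reuses this schedule.

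None of it supplies the missing check. Section 9.1.9 and Table 1 are legible and require no repeat before the dose. The shared 28-day window is not a good parallel, because an unsuspected conception can turn a correct negative result into a wrong one within that window. The protocol already repeats ECGs, chemistries and vital signs on Day -1.

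**Conclusion.** The concern holds. A site that follows the plan exactly may infuse tinostamustine 0 to 27 days after the only required pregnancy test, with nothing in the visible text requiring a retest of a woman not suspected to be pregnant and nothing requiring contraception before the dose. The gap follows directly from the schedule. How often it would be long, and how many women it would affect, cannot be determined from the documents.

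This is a low-frequency safety gap with an irreversible consequence and a very small cost to close. The sponsor should close it in any protocol that carries this schedule forward. It does not affect the statistical conclusions of the study.

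**What to change.** - **Section 9.1.9 and Table 1:** keep the screening hCG, which gives a check before any skeletal radiographs or MUGA scan. Add that the negative result relied on for exclusion 9 must come from a short interval before the Day -1 infusion, fixed by the sponsor, and must be reviewed before dosing. If the screening test is older than that, repeat a urine or serum hCG in women of childbearing potential. Show this as a conditional mark in the D-1 column.
- **Criterion 12:** state that contraception runs from informed consent through at least 90 days after dosing. This is needed as well as the retest, because no test excludes a conception too early to detect.

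**Cost.** One extra hCG for the few women tested early, one conditional mark in Table 1 and one edited criterion. No visit is added: patients attend on Day -1 and blood is already drawn then (footnote 16: "Blood samples for PK are to be collected immediately pre-infusion of tinostamustine"), and a urine test would also do. The drawbacks are an occasional late screen failure and up to 27 more days of contraception.
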